***Aim 3:***

We will evaluate the feasibility to collect and use passive data to track disease progression. Passive data collection will come in two flavors - displacement tracking that captures a participant's life space, i.e. their mobility patterns and collection of accelerometer and gyroscope readings when the participants are walking throughout the day. The walking data will be analyzed exactly the same as the actively collected data as described in Aim 2. The displacement tracking requires more care and will require us to first determine feasibility of data collection (Aim 3a) and extensive norming before assessing ability to track progression (Aim 3b).

Evaluation of Data Collection:

The first component of this Aim will focus on evaluating the feasibility of collecting passive data from individuals over a 2- year time period. This includes addressing two potential barriers to data collection: (1) Participant willingness to provide permission for passive monitoring and (2) the ability to collect passive data continuously over a 2-year period despite infrastructure changes caused by smartphone hardware and software upgrades.

*Hypothesis:* 70% of AT-HOME PD participants who participate in the smartphone component will consent to collection of passive data.

This will be evaluated by observing the number of active participants willing to enroll in this sub-study.

*Hypothesis:* Passive data will be collected in a persistent manner for the full 2-year study in at least 75% of consented individuals. Data collection will be monitored on a continuous basis.

We will evaluate the ability to use passive motor measures to predict relative changes in disease severity within a participant. Due to the highly individualized nature of activity patterns, it is unknown whether passive data can be used to derive absolute measures of disease severity. However, we expect that relative changes in activity patterns over time will provide a mechanism to track disease progression on an individualized basis. Features from displacement data such as total daily movement, number of daily trips, etc. will be generated and normed per individual before evaluation of disease progression using the same methods as described in SA 2b.

We will evaluate the use of passive measures to directly assess disease severity. The longitudinal nature of the displacement data provides the ability to identify personalized changes in disease burden over time and to evaluate whether changes in activity patterns over time are comparable to changes in disease severity as evaluated within the other components of this study. By focusing on changes in app active task performance and changes in tele-visit evaluations we can test the ability to track disease severity. Daily displacement will be evaluated per individual relative to: finger tapping, gait assessment, and overall composite score for smartphone-based motor evaluation using passive data collected during the burst periods using Lin's concordance correlation coefficient,  $r_c$ . Likewise we will perform the same analysis on the tele-visit assessments.

Anticipated outcomes and alternatives:

The overarching goal of Aim 3 is to evaluate whether and how passive data collection can be used for long-term monitoring of PD symptoms in clinical research cohorts. If we can observe relative changes in disease state, it could be used to trigger standard assessments – providing a way to reduce clinic burden and cost by deploying expensive clinic visits only when necessary rather than at regular time intervals. The use of these data also provides a mechanism to augment existing severity measures by directly evaluating the impact of disease on daily life. While not explicitly described in this proposal, the data collected within the program can be used to evaluate additional approaches to passive monitoring. For example, collection of accelerometer data provides the opportunity to develop an algorithm to monitor gait and balance from daily activities rather than formal assessments. Such assessments are exploratory for PD assessment but have demonstrated utility in the context of other neurological disorders.

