
Statistical Analysis (by Specific Aim)
	
SA 1: We will use results from the REACT-PD study to establish a calibration of tele-visit (TV) assessments to predict in-clinic MDS-UPDRS scores (Aim 1b). Lin's concordance correlation coefficient, <math>r_c</math>, will be used to summarize accuracy of the calibrated TV estimates vs. scores collected from in-person SURE-PD3 visits conducted close in time, accepting TV estimates as sufficiently accurate if <math>r_c > 0.8</math>. If we observe insufficient concordance, we will recalibrate using all available data from both REACT-PD and the current study.
 
SA 2: The study sample will be randomly split 2:1 into calibration and validation subsets. The calibration sample will be used to derive smartphone (SP) measures that best match the TV assessed composite scores of motor function (MDS-UPDRS part 3), non-motor function (MoCA total score), subjective function (including clinical global impression [CGI] scores, patient global impression scores, modified Schwab and England ADL scores, and MDS-UPDRS parts 1b and 2 scores), and estimates of MDS-UPDRS part 1-3 total scores (Aim 2a). The accuracy of calibrated SP measures will be tested in the reserved validation sample using Lin's concordance correlation coefficient, <math>r_c</math>. If we observe insufficient concordance, we will recalibrate using all available data from both the calibration and validation samples.
 
TV assessments and calibrated SP measures of disease progression will be compared generally and between specific subsets of participants expected to progress at different rates (Aim 2b). Each measure will be standardized to 30% of the observed mean change over 2 years based on a random-slopes linear mixed model of the full sample such that a one-unit change of all standardized, calibrated measures would reflect an equivalent magnitude of change relative to natural rates of progression. Estimated measure-specific variance components will be used to estimate the standard error for a treatment group comparison from a two-arm trial assuming an assessment schedule appropriate for a given measure, e.g., annual for TV measures and quarterly for SP measures. The ratio of squared standard errors will be used to estimate the relative sample size required using one or another measure for designs with equivalent power. The same approach will be used to identify measures that are sensitive to biological subgroups (e.g., among participants stratified by their rate of MDS-UPDRS progression over the first 2 years of in-clinic follow-up in the parent trials) or treatment-based subgroups (e.g., participants randomized to isradipine or serum urate elevation). TV assessments and SP measures will also be compared with respect to their accuracy in predicting future clinical events and changes in

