### 13.1 Data Processing and Quality Control (QC) for Smartphone (SP) Based Measures:

Data QC and cleaning: As data from the SP are deposited on a daily basis into Synapse, we will have a clear measure of compliance and engagement. Additionally, data streams can be monitored for quality. Data scientists and statisticians at Sage Bionetworks have developed an extensive pipeline to monitor and QC active task measurements from smartphone applications (e.g., <https://github.com/Sage-Bionetworks/mpowertools>). These tools will be adopted and expanded to monitor and QC passive data streams. During the development stage of the application we will run small scale internal experiments where user use Android and iOS devices concurrently to establish bounds on differences between devices.

Data processing/feature extraction: Quality processed data will be summarized into features using extensions of our feature extraction pipelines for active tasks. These include but are not limited to time and frequency domain statistics, energy and entropy of frequency spectrum from the tri-axial accelerometer, along with absolute displacement measurements. For displacement information (Aim 3b) data will be summarized into variables such as furthest distance traveled, frequency of trips, average daily distance etc. Also, additional specific features will be selected based on previously published

studies using passive data and expert knowledge of behavioral patterns of PD patients. These measures will be summarized to a single measure by training a n-fold cross-validated machine learning model using the discovery data subset. Additionally, features will be evaluated by test-retest reliability across time. Data analysis will be performed as described in SA 3.B and 3.C below.

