## 13.2 Statistical Analysis Plan

**Aim 1:** To evaluate concordance between in-clinic and tele-visit MDS-UPDRS assessments (Aim 1b), we will use results from the REACT-PD study to calibrate tele-visit assessments to in-clinic MDS-UPDRS scores, matching means and standard deviations cross-sectionally. We will use Lin's concordance correlation coefficient,  $r_c$ , to summarize accuracy of the calibrated tele-visit estimates vs. scores collected from in-person SURE-PD3 and SUPER-PD visits conducted close in time, accepting tele-visit estimates as sufficiently accurate if  $r_c > 0.8$ . If we observe insufficient concordance, we will investigate contributions of bias, scale difference, and imprecision and re-calibrate using all available data from both REACT-PD and the current study.

**Aim 2:** We will assess the calibration and correlation between tele-visit (TV) and SP metrics both cross-sectionally and longitudinally (Aim 2a). We will generate SP-derived metrics that best match composite scores of motor function (MDS-UPDRS part 3), non-motor function (MoCA total score), subjective function (including global impression (CGI) scores, Schwab and England ADL scores, MDS-UPDRS parts 1b and 2 scores, and estimates of MDS-UPDRS part 1-3 total scores. We will randomly split our sample 2:1 into calibration and validation subsets. For each measure, we will use the calibration sample to develop a transformation of SP data that best matches the TV measurement machine learning models using a variety of machine learning techniques with a final selection based on overall accuracy by 10-fold cross-validation. We will test the accuracy of calibrated SP measures in the reserved validation sample using Lin's concordance correlation coefficient,  $r_c$ . If we observe insufficient concordance, we will investigate contributions of bias, scale difference, and imprecision and re-calibrate using all available data from both the calibration and validation samples.

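### Aim 3 compares daily displacement with smartphone tapping, gait and the motor composite by Lin's concordance coefficient, with no common scale or direction stated for both sides

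*Combined protocol and SAP*

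**What the plan says.** Under Aim 3, section 13.2 asks whether displacement can assess severity directly. The purpose is to "evaluate whether changes in activity patterns over time are comparable to changes in disease severity". For the smartphone tasks the text reads "Daily displacement will be evaluated per individual relative to: finger tapping, gait assessment, and overall composite score for smartphone-based motor evaluation" and continues "using passive data collected during the burst periods using Lin's concordance correlation coefficient". It then adds: "Likewise we will perform the same analysis on the tele-visit assessments". That paragraph gives no transformation, common scale or sign convention.

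Scaling steps appear elsewhere:

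- **Section 13.2, Aims 1 and 2.** Aim 1 will first "calibrate tele-visit assessments to in-clinic MDS-UPDRS scores, matching means and standard deviations cross-sectionally". Aim 2 first transforms the smartphone data towards the tele-visit measure in the calibration sample. Lin's coefficient follows in both.
- **Section 13.2, Aim 3.** Displacement features are to be "normed per individual before evaluation of disease progression using the same methods as described in SA 2b". An earlier sentence under the same aim says more generally that displacement needs considerable norming before its ability to follow progression is assessed.
- **Synopsis, SA 2.** "Each measure will be standardized to 30% of the observed mean change over 2 years". This serves the comparison of standard errors between measures.
- **Section 13.1.** "These measures will be summarized to a single measure by training a n-fold cross-validated machine learning model using the discovery data subset". No training target is named.
- **Synopsis, SA 3.** The passive summary metric is matched with MDS-UPDRS part 3, Schwab and England, parts 1b and 2, and the parts 1-3 total, and then tested by Lin's coefficient in the validation subset. Tapping, gait and the smartphone composite are not listed.

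Section 13 opens by deferring further detail to a separate SAP, which takes precedence over the protocol.

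**The concern.** Lin's coefficient is high only when paired values are numerically close. It suits Aims 1 and 2, where one measure has been calibrated to the other. Distance travelled and tapping performance are different quantities in different units, and nothing in the text puts them on one scale or says which direction counts as worse for each.

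The statistic also does not fit the question. Aim 3 doubts that passive data give an absolute measure of severity and expects relative change within a person to be informative. That is a question of association over time. Working with changes instead of levels does not help, because changes still carry units, spread and sign.

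At stake is the stated analysis of whether displacement tracks motor function. A marker that tracked it closely could be reported with a coefficient near zero or below zero, and the value would move with the unit chosen.

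**Working it through.** The plan states no figure for this comparison, so there is none to reproduce. The check uses the definition of the coefficient:

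r_c = 2·r·s1·s2 / (s1² + s2² + (m1 − m2)²)

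Here r is the ordinary correlation, and m and s are the means and SDs. The documents give no means, SDs or correlations for these measures, so **all means and SDs below are illustrative assumptions**.

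**1. Raw levels, r = 1.** Displacement 10 km (SD 5), taps 150 (SD 30).
- Kilometres: 2·5·30 / (25 + 900 + 140²) = 300 / 20,525 = 0.015.
- Metres: 300,000 / (25,000,000 + 900 + 9,850²) = 300,000 / 122,023,400 = 0.002.
- Miles: 0.009.
- Over tap means of 50 to 200 and SDs of 5 to 50, the kilometre value runs from 0.001 to 0.12.

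**2. Only displacement normed, r = 1.** z-scored displacement against raw taps: 2·1·30 / (1 + 900 + 150²) = 60 / 23,401 = 0.003. Norming one side does not create a common scale.

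**3. Raw changes, r = 1.** −1 km (SD 3) against −5 taps (SD 15).
- Kilometres: 2·3·15 / (9 + 225 + 4²) = 90 / 250 = 0.36.
- Metres: 90,000 / (9,000,000 + 225 + 995²) = 0.009.

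**4. Direction not aligned, r = −1.** Displacement 10 (SD 5) against a score of 25 (SD 10): −100 / (25 + 100 + 225) = −0.29.

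**5. SA 2 standardisation extended to this comparison, r = 1.** Mean changes become equal, but spreads need not. With SDs in ratio 1:2, r_c = 4/5 = 0.80; with 1:5, 10/26 = 0.38.

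**6. Both sides z-scored.** 2r / (1 + 1 + 0) = r. The scale problem disappears. If direction is still reversed, a strong association shows as, for example, −0.90 at |r| = 0.9.

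**7. Precision at zero association.** The text does not say whether per individual means one coefficient per person. If it does, the 95% ranges for one person, by simulation with independent observations, are about:
- ±0.83 from 3 tele-visits;
- ±0.58 from 9 burst means;
- ±0.21 from 90 paired days (9 bursts × 10 daily sets).

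A pooled within-person correlation with N people and k occasions has a range of about ±1.96/√(N(k − 1)). Section 4.1.1 expects about 240 passive-data participants, and the 75% persistence hypothesis in section 13.2 gives 240 × 0.75 = 180.
- 3 tele-visits: 1.96/√480 = 0.09 with 240 people; 1.96/√360 = 0.10 with 180.
- 9 bursts, 180 people: 1.96/√1,440 = 0.05.
- 6 bursts, the section 6.5 standard for a successful participant, 180 people: 1.96/√900 = 0.065.

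**The case against.** The strongest reply is that the plan does mean to scale displacement. The general norming sentence in Aim 3 is not tied to SA 2b and can fairly be read as covering this comparison. Section 13.1 also builds a single machine-learning measure; if that model is trained on the comparator, concordance is reasonable. Raw kilometres against raw tap counts would be an unlikely analysis, and scale and sign conventions are ordinary content for the separate SAP. Once both sides are standardised, concordance equals correlation, so one added sentence could be enough.

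Much of this stands. It would be wrong to say that no scaling of displacement is planned, or that the protocol commits to raw units. What remains is that the described norming touches one side only, no step fixes the comparators' scale or the sign, and the machine-learning target is unnamed. Step 2 of the working shows that one-sided norming does not repair the coefficient.

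A reader might also infer that the tele-visit comparison has the same defect. The documents do not support that. The synopsis matches the passive metric to tele-visit scores in a discovery and validation split modelled on the active tasks, and the natural reading is calibration followed by concordance. Nor does the text establish that one coefficient per person from three visits is intended.

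**Conclusion.** The point holds for daily displacement against finger tapping, gait and the smartphone motor composite. For these, the documents name an absolute-agreement statistic without a two-sided scale or a direction, so its value would depend on units, spread and sign and would not answer the within-person question. The dependence follows from the formula; the particular values rest on assumed means and SDs and are mostly worst cases with raw units.

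The reach is modest. Section 2.1 words Aim 3 as exploration, and no concordance threshold is attached to displacement. The consent and persistence hypotheses, the walking-data analysis and the SA 2b progression analyses are unaffected, so a reader who concluded that Aim 3 as a whole fails would go too far. The separate SAP is not among the documents, so the finding is that the scaling is not stated in them. It should be corrected before analysis, since the choice of scale determines the result.

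**What to change.** In section 13.2, Aim 3, or in the separate SAP:

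1. For displacement against tapping, gait and the smartphone composite, replace Lin's coefficient with a pooled within-person association. A repeated-measures correlation, or a mixed model of the motor measure on person-centred displacement, would do. Report a 95% confidence interval and state the expected sign for each comparator in advance.
2. If Lin's coefficient is kept, standardise both measures within person and align direction first, or restrict it to outputs calibrated to the comparator in the discovery subset. In the latter case, name the training target of the single measure in section 13.1.
3. For tele-visit scores, say whether the matching step in the synopsis is a calibration. If so, keep concordance. If not, use the pooled within-person analysis rather than one coefficient per person from three visits.
4. Say what per individual means in this paragraph, and make the synopsis and section 13.2 agree.

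The cost is wording and routine analysis of data already planned for collection.

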Main Exclusionary Criteria	1. Inability to carry out study activities as determined by study staff
Study background and Rationale	At the launch of AT-HOME PD the STEADY-PD III and SURE-PD3 trials were active NINDS-funded phase 3 studies of potential disease-modifying interventions in PD. The long-term observation of participants from these trials, while challenging to implement, was deemed a valuable research opportunity. The reliance on in-person visits and snapshot assessments in a condition characterized by variable symptoms is an important limitation. Tele-visit, web-based surveys, and smartphone-based remote sensor assessments represent particularly promising methods for streamlining study conduct, reducing participant burden, and enabling the collection of data beyond the usual episodic, in-clinic assessments. The objective of this study is to leverage modern technology to develop, pilot and implement a 100% virtual model for long-term follow-up utilizing tele-visit and smartphone platforms for quantitative monitoring of clinician- and patient-reported outcomes (PROs).
Study Platforms and Outcome Measures	
Tele-visit platform – Participants will complete a total of three tele-visits, which will occur at baseline, month 12, and month 24. Some activities will be completed either prior to or post tele-visit by the participant. Assessments will include:
 
 
• Review of reportable events
 
• Review of concomitant medications
 
• MDS-UPDRS parts 1a, 3, and 4 (where applicable)
 
• Montreal Cognitive Assessment (MoCA)
 
• Schwab & England Activities of Daily Living Scale (SEADL)
 
• Clinician Global Impression and Patient Global Impression – Severity and Change
 
• Determination of Falls
 
• Performance of one complete set of active motor and cognitive smartphone application tasks (when applicable)
 
• Review of completion of MDS-UPDRS parts 1b and 2, self-reported falls, and patient global impression – severity and change (with direct link to survey sent ahead of visit)
 
• Review of compliance with smartphone tasks and FI assessments where applicable
 
• Preference and Burden Survey
 

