- **Smartphone platform (mPower-based app)** – The mPower application captures sensor data within the context of self-administered activity tasks (motor and cognitive). Processed sensor data is converted into multiple features that are evaluated individually and in aggregate as digital biomarkers for disease severity. Building on experience gained in the mPower and Smart4SURE studies, a new application will be deployed to assess motor and cognitive functions sensitive to PD progression (see SOA; Table 2). The mPower 2.0 app is compatible with Android as well as iPhone devices, and has been modified to allow passive collection of gait and mobility data with participant permission (for SA3). The application will include a defined set of tasks; described below under Study Procedures. As per the SOA, participants will be asked to complete a four to six-minute battery of motor tasks daily for at least 10 days and an eight-minute battery of cognitive tasks daily for at least 3 days within a two-week period every quarter. The two-week burst will be considered successful if we are able to collect at least 10 daily activities and can be extended by 5 days if this minimum is not met.

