## 4. STUDY POPULATION

### 4.1 Participant Numbers

#### 4.1.1 AT-HOME PD Participants

Approximately 420

All individuals with early idiopathic PD enrolled in the STEADY-PD III (NCT02168842) and SURE-PD3 (NCT02642393) studies (N~600) who have consented to be contacted for future research will be asked to participate. We expect approximately 70% of them (N~420) to consent and participate in at least the tele-visit portion of the study. We expect approximately 80% of enrolled individuals (N~340) to participate in the smartphone portion (and thus the smartphone vs tele-visit comparison) of the study. We expect approximately 70% of participants in the smartphone portion (N~240) to consent to passive data collection (and thus contribute to Aim 3). We expect approximately 80% of enrolled individuals (N~340) to participate in the FI portion of the study.

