If AT-HOME PD study participants will be considered for any future follow up research their contact information will be obtained from the University of Rochester (UR) secure HIPAA compliant database based on original consent. If the subject declined contact in the original study, the subject will be allowed to contact the UR AHPD study team directly with an interest in study participation.

Considering the low participant burden of remote data collection, an inherent advantage of the outcome measures under investigation, we anticipate a modest dropout rate of ~15% from the tele-visit component over the two-year extension study. In addition, recruitment and retention will be motivated by multiple tested strategies ranging from reasonable reimbursement payments (to be paid in three installments following each tele-visit via check) to regular communication with participants.

Formative research through patient interviews indicates that long-term data collection in a remote setting will only be sustainable with a smartphone application that is specifically designed to meet the needs and interests of the participant population. Based on initial interviews, engagement strategies will focus on altruism, self-exploration, education, and community. These are implemented through the application using news feeds, infographics, participation dashboards, and notifications. Importantly, participants will be provided with the option to view the outcomes of their assessments in a manner that was highly effective at promoting engagement within mPower but was not feasible during the smartphone sub-study (Smart4SURE) of SURE-PD3.

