#### d. Smartphone Sessions (Baseline, Month 3, 6, 9, 12, 15, 18, 21, 24)

- 14-day smartphone sessions will occur on a quarterly basis.
- Given diurnal variation in active task performance, participants will be asked to select morning or afternoon as their preferred window for completion and to consistently attempt to complete the active tasks according to their selected preference.
- Participants will be notified one day before the start of each 14-day session

During these 14-day sessions, participants will be asked to complete daily 4 to 6-minute smartphone-based motor tasks. If they fall behind and are not able to complete at least 10 daily activity sets they can optionally continue for up to 5 additional days.

The following motor activities will be completed by the participant:

- Gait Task
- Finger Tapping Task
- Resting Tremor Task

- Balance task

During these 14-day sessions, participants will be asked to complete an approximately 8-minute set of smartphone-based cognitive assessments on at least 3 of the days.

The following activities will be completed by the participant:

- Digit Span
- Digit Symbol Substitution Tests
- Spatial Working Memory

Participants will be asked to provide basic demographic information through the application once. Participants will also use the application to track their medication adherence relative to tasks and, optionally, self-reported symptoms and triggers. Additionally, participants may perform the active tasks at any time outside of the 14-day smartphone sessions if desired.

Compliance will be actively monitored.

- Participants will receive reminders if they do not perform the activities for two consecutive days and/or after not performing the activities for four days of the 14-day session.
- Participants who enable notifications will receive daily notifications during each 14-day session
- Sage Bionetworks will make quarterly reports available to CHeT/CTCC that will include each participant's compliance status.

e. FI Sessions (Baseline, Month 3, 6, 9, 12, 15, 21, 24)

- AT-HOME PD participants will be asked to complete a set of standard questionnaires through a companion study called FI, (<https://foxinsight.michaeljfox.org>).
- Participants will be asked to complete the questionnaires in the SOA every 90 days. [Refer to SOA] The baseline visit takes approximately one hour to complete; subsequent visits take only 10-15 minutes to complete.

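### In Aim 3 the per-person Lin's r_c is extended to tele-visit scores, but three tele-visits per person are too few for any individual coefficient to be interpreted

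*Combined protocol and SAP*

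**What the plan says.** Section 13.2, Aim 3, sets the unit of analysis for displacement: "Daily displacement will be evaluated per individual relative to: finger tapping, gait assessment, and overall composite score for smartphone-based motor evaluation". The statistic and data window follow: "using passive data collected during the burst periods using Lin's concordance correlation coefficient". The next sentence extends this to the clinician-rated data: "Likewise we will perform the same analysis on the tele-visit assessments".

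The synopsis fixes the number of clinician-rated time points: "Participants will complete a total of three tele-visits, which will occur at baseline, month 12, and month 24". The section on recruitment and retention adds that "we anticipate a modest dropout rate of ~15% from the tele-visit component over the two-year extension study". By contrast, section 5.5 schedules nine quarterly smartphone sessions, and in each "participants will be asked to complete a four to six-minute battery of motor tasks daily for at least 10 days". On the size of the passive-data group, section 4.1.1 says: "We expect approximately 70% of participants in the smartphone portion (N~240) to consent to passive data collection".

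For the tele-visit version of this step, section 13.2 gives no pooling rule, no minimum number of pairs, no confidence interval and no repeated-measures form of r_c. Section 13.4 gives no precision for it.

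**The concern.** The same method is applied to two limbs with very different amounts of data per person. The smartphone limb offers nine session averages, or about 90 daily pairs, for each participant. The tele-visit limb offers three pairs, and fewer for anyone who misses a visit. This holds even if displacement and the clinical score have been brought to a common scale.

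Aim 3 hopes to follow change on an individualised basis, and suggests that passive data might one day trigger standard assessments. If the tele-visit step is carried out as worded, each participant gets a coefficient that looks like an individual result but is mostly sampling noise. Many people in whom displacement truly follows the clinical score would appear not to be tracked.

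**Working it through.** **Inputs.** Tele-visits per person: 3 (synopsis). Smartphone sessions: 9 (section 5.5), with at least 10 motor-task days each (section 3.1, Study Platforms), so 9 x 10 = 90 daily pairs. Passive-data participants: about 240 (section 4.1.1). Tele-visit dropout: about 15% (section 5.1). Persistent passive data: at least 75% of those who consent (hypothesis in section 13.2, Aim 3).

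**Nearest figure in the plan.** There is no stated precision for this step to reproduce. The closest is SA 2a in section 13.4: n about 115, threshold 0.80, true concordance 0.87, power 80%. With Fisher's z, power = Phi[(atanh 0.87 - atanh 0.80) x sqrt(n - 3) - 1.645] = Phi[0.2345 x sqrt(112) - 1.645] = Phi(0.837) = 79.9%. A one-sided 0.05 test therefore reproduces the plan's figure; a two-sided test gives 69.9% and does not.

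**Same framework at n = 3.** The standard error 1/sqrt(n - 3) is undefined. With n - 2 in place of n - 3, an observed 0.87 has a 95% interval of about -0.56 to 1.00, and power against 0.80 is Phi(0.2345 - 1.645) = Phi(-1.41), about 8%. Even a Pearson correlation on three points must exceed 0.988 (one-sided) or 0.997 (two-sided) to differ from zero at 0.05.

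**Simulated r_c for one person.** Assumptions: bivariate normal, independent pairs, equal means and SDs. There were 200,000 replicates for 3 and 9 pairs, and 40,000 for 90 pairs.

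| Pairs | True concordance | Central 95% range | Mean | P(r_c > 0.8) |
|---|---|---|---|---|
| 3 | 0 | -0.83 to 0.83 | 0.00 | 3% |
| 3 | 0.5 | -0.69 to 0.94 | 0.30 | 13% |
| 3 | 0.8 | -0.44 to 0.98 | 0.57 | 37% |
| 3 | 0.87 | -0.31 to 0.99 | 0.67 | 49% |
| 9 | 0.87 | 0.51 to 0.96 | 0.82 | 69% |
| 90 | 0.87 | 0.81 to 0.91 | 0.87 | 98% |

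At three pairs, the ranges for no concordance and for strong concordance largely overlap. At nine or 90 pairs the coefficient becomes usable.

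**Average over people.** The SD of the individual r_c at three pairs is 0.44 at true 0 and 0.39 at true 0.8. The standard error of a mean over 240 people is 0.44/sqrt(240) = 0.028 or 0.39/sqrt(240) = 0.025. Means of 0.00 and 0.57 are thus clearly separated, but 0.57 understates 0.8.

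**Precision of a pooled within-person correlation.** Each complete participant contributes 3 - 1 = 2 within-person degrees of freedom. The approximate half-width (for a correlation near zero) is 1.96/sqrt(df).
- 240 complete: df = 480, half-width 0.09.
- 240 x 0.75 = 180 complete: df = 360, half-width 0.10.
- 180 x 0.85 = 153 complete, if the two losses are independent: df = 306, half-width 0.11.

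**The case against.** **Other analyses cover the question.** Section 13.2 also normalises displacement features within each participant and sends them to the SA 2b methods, which use a bivariate random-slopes mixed model for pairs of tele-visit and smartphone measures. The synopsis for SA 3 uses r_c in the validation subset, that is, across participants. It stands that this step is not the only route to the longitudinal question. But SA 2b uses the model's variance components to compare standard errors for a future trial, and the synopsis r_c answers a between-person question. Neither replaces the per-person step.

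**The wording may be loose.** Per-individual evaluation could be shorthand for normalisation within the individual. That is possible, but it is not what the sentence says. If it is meant, the text still needs an edit.

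**Nothing hangs on the coefficients.** Aim 3 is framed as exploratory, no threshold classifies anyone as tracked or not, and the only power statement for SA 3 concerns a ROC AUC. Section 13 also defers detail to a separate SAP that takes precedence. This stands, and it limits the severity.

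**A stronger reading fails.** A reader might infer that a useless measure would produce many apparent good trackers. About 20% of people would indeed show a three-point Pearson correlation above 0.8 with no association: (1 - (2/pi) x asin 0.8)/2 = 0.205. The plan specifies r_c, however, for which the figure is 3%. The 20% would carry over only if both series were standardised within person, and the documents describe that for displacement, not for tele-visit scores.

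**Conclusion.** The point holds for the tele-visit limb only. With three pairs per person, an individual r_c cannot distinguish tracking from no tracking: the 95% ranges are -0.83 to 0.83 and -0.44 to 0.98 at true values 0 and 0.8, and 63% of people would fall at or below 0.8 when 0.8 is the truth.

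A reader might go further and conclude that the whole set of some 240 coefficients is worthless. That is not supported. Their mean separates 0 from 0.8, although with a downward bias. What fails is inference about a single person, and an unadjusted average taken as an estimate of concordance.

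The figures assume normal, independent pairs with equal means and SDs. Any remaining difference in location or scale would lower r_c further. An extra unscheduled or withdrawal tele-visit could occasionally give a fourth pair, but the Fisher interval around an observed 0.87 would still run from -0.56 to 1.00. Severity is moderate, because the step is exploratory and carries no decision rule.

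**What to change.** In section 13.2, Aim 3 (or in the separate SAP), replace the sentence that carries the per-person analysis over to tele-visits. Specify instead one pooled within-person analysis: a mixed model, or a repeated-measures correlation, of tele-visit score on person-centred displacement across all passive-data participants. Report a single within-person slope and correlation, each with a 95% confidence interval. State in advance whether time since baseline enters the model, since that decides whether a shared trend counts as tracking. Keep individual-level r_c summaries for the smartphone limb only. If the authors meant only that displacement is normalised within person, the text should say so and name the unit over which r_c is computed.

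The cost is a wording change. No visit, assessment or data item is added. The downside is that individual tele-visit coefficients are no longer reported.
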